- Mean SBP from T-182d to T-0d (+/- 10 mm Hg)
- Number of office visits to primary care in the past year categories : 1, 2, 3-4, 5+

Assess for time 0 (11/19/2020)

Characteristics of study populations and matched control populations.

At time 0, 1 month (12/18/2020), 3 months (2/18/2020) and 6 months (5/18/2020) describe for each group:

- The proportion of patients who satisfy the performance measure Controlling High Blood Pressure (NQF 0018)
- The systolic blood pressure at the most recent face-to-face office visit

At time 1 month (12/18/2020), 3 months (2/18/2020) and 6 months (5/18/2020) describe for each group:

- Number of antihypertensive medication intensifications between the study start and the measure date

Hypothesis testing—perform separately for primary and secondary populations

H1: Antihypertensive medication intensification will be greater in pilot clinic(s) with RPM compared to contemporaneous control clinic(s).

Compare at 1, 3, and 6 months the number of medication intensifications between study group and control group using Poisson regression (if variance of medication intensifications is approximately equal to the mean) or otherwise negative binomial regression with study group as the independent variable.

H2: The proportion of patients who satisfy the performance measure Controlling High Blood Pressure (NQF 0018) will be greater in pilot clinic(s) with RPM compared to contemporaneous control clinic(s).

Compare at 1, 3, and 6 months the proportion of patients in the study group and control group who satisfy the performance measure Controlling High Blood Pressure (NQF 0018) using logistic regression with study group and baseline systolic blood pressure as independent variables.

H3: The systolic blood pressure at the most recent office visit will be lower in pilot clinic(s) with RPM compared to contemporaneous control clinic(s).

Compare at 1, 3, and 6 months the systolic blood pressure at the most recent face-to-face office visit among patients in the study group and control group using linear regression with study group and baseline systolic blood pressure as independent variables.

RPM enrolled patient analyses

We will explore the trajectories of blood pressure for individuals who are prescribed RPM.

We will describe all patients who are enrolled in RPM at their enrollment date and follow their blood pressure outcomes at 1, 3, and 6 months from their enrollment (or until the study end date).

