We will retrospectively, at the end of the study end date, identify matched controls (4:1) for patients enrolled in RPM selected from patients in the non-pilot clinics and matched on the same baseline criteria (assessed at the time of RPM ordering). We will perform comparisons analogous to those described above for the primary cohort.

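### The RPM-patient comparison targets patients prescribed RPM and matches at ordering, but admits only enrollees, so any loss between order and enrollment selects the RPM arm alone

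*SAP*

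**What the plan says.** The point concerns the closing section of the SAP, *RPM enrolled patient analyses*, which makes these statements:

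- **Aim:** "We will explore the trajectories of blood pressure for individuals who are prescribed RPM".
- **Patients described:** "We will describe all patients who are enrolled in RPM at their enrollment date". Their blood pressure is followed at 1, 3 and 6 months, counted from enrollment, or to the study end date.
- **Controls:** found retrospectively at study end, as "matched controls (4:1) for patients enrolled in RPM selected from patients in the non-pilot clinics".
- **Timing of the matching criteria:** "assessed at the time of RPM ordering".
- **Use:** "We will perform comparisons analogous to those described above for the primary cohort". The section therefore goes beyond description to between-group comparisons of the H1 to H3 type.

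The SAP does not say whether prescription, ordering and enrollment are one event or several. It gives no rule for a patient with an order who never enrolls, and no date from which a control's follow-up is counted.

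**The concern.** Membership of the RPM arm depends on enrollment, while the matching criteria are assessed at ordering. If the two events differ, a patient whose clinician orders RPM but who declines, cannot be reached or never starts is left out because of something that happened after matching. A control in a non-pilot clinic passes no such step, so an equally reluctant or unreachable control stays eligible.

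Patients who complete enrollment are plausibly more engaged: more likely to attend, to accept a medication change and to take the medication. Each of these bears on the outcomes compared, namely intensifications, the blood pressure control measure and SBP. The contrast could then lean towards RPM even if RPM had no effect. It would also describe enrollees, whereas the section says its interest is in patients prescribed RPM.

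The index dates add a second difficulty. Matching belongs to the order date and follow-up to the enrollment date, and the controls have no stated start of follow-up. Moving the follow-up clock to the order date would resolve this but would not bring back the patients who never enrolled.

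**Working it through.** The SAP gives no order-to-enrollment rate and no figure for this analysis, so there is nothing to reproduce. The check compares the statements and then works out the size on assumed values.

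**Step 1. Population and dates in the same section**

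| Element | RPM arm | Controls |
|---|---|---|
| Stated target | prescribed RPM | not applicable |
| Who is included | enrolled in RPM | matched patients in non-pilot clinics |
| Matching criteria assessed | at ordering | date not stated |
| Description and follow-up start | at enrollment | not stated |
| Condition after matching | must enroll | none |

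The last row is the asymmetry. It matters only if ordering and enrollment are separate events with some loss between them.

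**Step 2. Does the plan already remove the selection?** The matching criteria are sex, age, mean SBP in two windows over the preceding year, and number of primary care visits in that year. The visit category captures some past engagement, but not acceptance or completion of RPM enrollment. In the models to be carried over, H1 has study group as its only independent variable, and H2 and H3 add baseline SBP. None of them represents willingness to enroll. Matching and adjustment can therefore reduce the selection but not eliminate it.

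**Step 3. Size for SBP**

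Let f be the share of ordered patients who never enroll. Let m be the mean follow-up SBP of enrollees, and m + d that of non-enrollees, where d arises for reasons unrelated to RPM.

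- Mean over all ordered patients: (1 − f) × m + f × (m + d) = m + f × d.
- Mean over enrollees only: m.
- Shift from restricting to enrollees: m − (m + f × d) = −f × d.

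Controls pass no such filter, so the contrast moves by the same amount, towards RPM when d is positive. Neither f nor d is in the SAP. On assumed values:

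| | d = 2 mm Hg | d = 5 mm Hg | d = 8 mm Hg |
|---|---|---|---|
| f = 0 | 0 | 0 | 0 |
| f = 10% | 0.2 | 0.5 | 0.8 |
| f = 20% | 0.4 | 1.0 | 1.6 |
| f = 40% | 0.8 | 2.0 | 3.2 |

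These shifts are before any reduction from matching or adjustment. The part of d explained by the matching factors or baseline SBP is at least partly removed, so the shift that remains would be smaller. No comparable figure is given for intensification or the control measure, because the SAP supplies nothing on which to base one.

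**The case against.** The strongest reply is that this is an analysis of enrolled patients with one loose word. The section heading and the sentences that define the patients and their controls all say enrolled; prescribed appears once, in the introduction. The protocol may describe how an order becomes an enrollment, and if the terms name one event the bias is zero. This stands as a limit on the claim. It does not remove the need to act, because the SAP refers to both an enrollment date and a time of ordering and does not equate them.

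A second reply is that the analysis is exploratory and that studying actual users is legitimate alongside a clinic-level comparison. That is fair for the descriptive part. It carries less weight for the between-group comparisons the section also plans, where the asymmetry operates.

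A third reply is that an order is itself a clinician's choice that controls in non-pilot clinics never face, so taking all ordered patients leaves some selection in place. This is correct. The change removes the avoidable part, between order and enrollment, and no more.

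A reader might also infer more than the text supports:

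- **That the whole baseline is set at ordering.** Only the matching criteria are; description and follow-up start at enrollment.
- **That H1 to H3 are biased.** Those tests compare cohorts defined at 11/19/2020 in pilot and control clinics, and no one leaves them for failing to enroll.
- **That patients who stop RPM are dropped.** The SAP nowhere excludes them.

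**Conclusion.** The concern holds in conditional form and only for the supplementary RPM-patient comparison. The stated target, the patients admitted and the date of matching do not agree. If some orders do not lead to enrollment, the RPM arm is selected after matching and the control arm is not.

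The direction, favouring RPM, is plausible but not shown; it rests on non-enrollees having worse outcomes for reasons unrelated to RPM. The size for SBP is f × d: 0.2 to 3.2 mm Hg over the assumed range, before any reduction from matching or adjustment, and zero if every order leads to enrollment. A reader might take this range as a measured bias, but both inputs are assumptions and the SAP does not show that any patient is lost between order and enrollment.

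**What to change.** For the between-group comparison in *RPM enrolled patient analyses*:

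1. Define the RPM group as all patients with an RPM order in the study period, and keep them in the analysis whether or not they enroll.
2. Use the order date as the single index date for matching and for the 1, 3 and 6 month follow-up, and give each matched control the index date of its RPM patient.
3. Report the numbers ordered and enrolled.
4. Keep the enrolled-only comparison as a secondary analysis labelled as selected.
5. State as a limitation that selection by the clinician's decision to order RPM remains.

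The cost is SAP wording, an extract of all RPM orders instead of only those of enrollees, and one more matched set. Order dates are already needed for enrollees, and controls are in any case identified only at study end. The estimated effect will probably be smaller than among enrollees alone.
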